**A Mechanistic Perspective on Post-Activation Performance
Enhancement Responsiveness: A Randomized Controlled
Study of Acute Changes in Muscle Architecture, Contractile
Property Kinetics, and Muscle Excitability**

NCT06982937

18.05.2025

Objectives and endpoints.

The primary objective is to test whether a heavy conditioning activity (CA; one set of 2–3 repetitions at ~90% 1RM) produces post-activation performance enhancement (PAPE) in countermovement jump (CMJ) height compared with a control treadmill warm-up within the 4–12 min window after the intervention. The analysis does not assume *a priori* when the maximal effect occurs; instead, the minute of maximal between-group difference (denoted T^*) will be identified empirically. The primary endpoint is the change in CMJ height from baseline (ΔCMJ) at post-intervention time points (4, 6, 8, 10, 12 min). Secondary endpoints include the time-course of ΔCMJ within the experimental group (EXP), individual responder status at each time point, and the associations between neuromuscular phenotype—estimated as %MHC-I from tensiomyography (TMG)—and the magnitude, timing, and likelihood of response. Ultrasound (USG) morphology (muscle thickness, pennation angle, derived fascicle length) will be analysed in parallel to performance endpoints. Electromyography (EMG), where available, will be treated analogously to USG/TMG (see below).

Data handling and derived variables.

At each time point, CMJ height is the mean of three trials; ΔCMJ and percentage change (% ΔCMJ) will be computed relative to baseline. Individual response is classified using MDC. USG outcomes will be averaged across three images; fascicle length is calculated as thickness divided by the sine of pennation angle (degrees converted to radians). TMG-based %MHC-I is estimated from delay, contraction, and half-relaxation times using the published multivariable model; TMG amplitudes and time constants may also be expressed as Δ or % Δ . If EMG is collected, signals will be band-pass filtered, rectified, quantified with 50-ms RMS, normalized (to MVC or M-wave), and summarized over task-relevant phases; % Δ at 4–12 min is computed analogously. Values >3.5 SD from group-time means will be flagged; primary analyses include all data, with winsorized sensitivity checks reported only if inferences change. Missing data will be not imputed for the primary analysis; mixed-effects models accommodate missingness assuming MAR.

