Primary analysis and identification of the peak time (T^*).

The confirmatory analysis uses a RM-ANOVA with ΔCMJ as the outcome, Group (EXP vs CON), Time (time effect: 4, 6, 8, 10, 12 min), and Group \times Time. If the interaction is significant, we estimate adjusted between-group contrasts at each minute with Bonferroni correction across the five time points. T^* is defined as the minute showing the largest positive EXP–CON difference in estimated marginal means (EMMs) with the smallest p-value. We report the EMM difference at T^* (95% CI) and effect size (d’Cohen). Greenhouse–Geisser correction if needed.

Within-group time-course and kinetics.

To describe the temporal profile without prespecifying a target minute, we analyse ΔCMJ across time within EXP using a one-way repeated-measures ANOVA (or LMM if assumptions are violated), followed by Bonferroni-adjusted pairwise EMMs to locate the within-group peak. To characterise response timing at the individual level, we model time to first and time to peak response (4–12 min) using Kaplan–Meier curves with censoring at 12 min, compare strata by log-rank tests, and fit Cox proportional-hazards models to estimate hazard ratios (HR, 95% CI) and concordance (C-index). This kinetics framework provides an assumption-light estimate of when athletes typically express PAPE.

Responder analyses and discrimination.

Responder distributions (Positive/neutral/adverse) will be compared between EXP and CON at each minute using likelihood χ^2 test. For mechanistic discrimination at specific minutes (including T^* once identified), we fit logistic models with %MHC-I as a continuous predictor and report ORs (95% CI),

Nagelkerke R², AIC, Hosmer–Lemeshow calibration, and ROC-AUC with sensitivity, specificity, and Youden's J cut-offs. Moderation analysis also will be used with simple slope analysis.

Phenotype and morphology linkages (USG/TMG/EMG).

Associations between %MHC-I and Δ CMJ will be quantified at each minute using Pearson's r. USG variables (thickness, pennation angle, fascicle length) will be analysed with the same three lenses applied to performance: (i) within-EXP time-course (rmANOVA/LMM with Tukey), (ii) responder linkage at each minute (one-way ANOVA or robust alternative; Hedges' g for P vs X), and (iii) phenotype linkage (correlations and moderation models). TMG (e.g., Dm, Tc, Tr) and EMG (e.g., normalized RMS, median frequency) follow this identical framework to ensure coherence across modalities.

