Moderation and mediation (pre-specified).

All moderators and predictors will be mean-centered; multicollinearity is checked (VIF < 5). Primary moderation models test whether (a) baseline CMJ modifies the effect of %MHC-I on Δ CMJ and (b) baseline morphology (thickness, pennation angle, fascicle length) modifies the effect of baseline CMJ on Δ CMJ. Significant interactions will be decomposed with simple slopes at -1 SD, mean, and +1 SD, with 95% CIs via nonparametric bootstrap (1,000 resamples) and publication-ready interaction plots. Exploratory mediation tests whether acute morphological change (e.g., % Δ thickness at a given minute) transmits baseline morphology effects to % Δ CMJ; indirect, direct, and total effects will be estimated by bootstrap (5,000 resamples; bias-corrected CIs) and interpreted cautiously.

Assumptions, multiplicity, and robustness.

Model diagnostics include residual normality (Shapiro–Wilk), homoscedasticity (residual–fitted patterns, Breusch–Pagan), linearity, and independence by design. Sphericity is tested for rmANOVA (Mauchly) with Greenhouse–Geisser corrections as needed. If mechanistic variables are skewed, appropriate transformations (e.g., log for EMG amplitude) are considered; otherwise we rely on LMM robustness. Multiplicity is controlled via Holm across the five between-group contrasts, FDR for correlation families, and restraint in post-hoc testing; moderation/mediation will be estimation-focused with full interval reporting and are not used to redefine the primary inference.

Reporting, visualization, and software.

We report means \pm SD with 95% CIs; between-group effects as Hedges' g; within-subject effects as d_{nZ} ; ANOVA-style effects as η^2 ; logistic results as ORs with AUC; and survival results as HRs with concordance. Figures include EMM trajectories with 95% CIs, individual waterfall plots with MDC bands, ROC curves for %MHC-I, Kaplan–Meier curves for first/peak response, interaction plots for significant moderations, and path diagrams for supported mediations. Analyses will be performed in Jamovi 2.6 and STATISTICA 13.1.

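### The difference and Cohen's d at T* come from the same data that select T* as the largest of five differences after a significant interaction, so they tend to be too large

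*Combined protocol and SAP*

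**What the plan says.** The Objectives and endpoints section leaves the peak minute open: "the minute of maximal between-group difference (denoted T^*) will be identified empirically". The candidates are 4, 6, 8, 10 and 12 min.

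The primary-analysis section then sets out three steps:

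- The per-minute contrasts are conditional: "If the interaction is significant, we estimate adjusted between-group contrasts at each minute with Bonferroni correction across the five time points".
- The peak is chosen from them: "T^* is defined as the minute showing the largest positive EXP–CON difference in estimated marginal means (EMMs) with the smallest p-value".
- The result at that minute is reported: "We report the EMM difference at T^* (95% CI) and effect size", the effect size being Cohen's d.

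The section on responder analyses carries the chosen minute forward: "For mechanistic discrimination at specific minutes (including T^* once identified), we fit logistic models".

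The section on assumptions, multiplicity and robustness says "Multiplicity is controlled via Holm across the five between-group contrasts", where the primary-analysis section names Bonferroni for the same contrasts. The reporting section plans "between-group effects as Hedges' g" and states "Figures include EMM trajectories with 95% CIs". Bootstrap is planned for simple slopes and mediation only. Nothing in the plan corrects the T* estimate for the way in which T* is chosen.

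**The concern.** Choosing the largest of several noisy differences and then reporting it from the same data favours the minute that chance has pushed up. Requiring a significant interaction first is a second selection, because it favours trials in which the five differences happen to be widely spread. Multiplicity adjustment limits false positives among the five tests. It does not move the point estimate or d.

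The T* difference, its interval and d are the only between-group estimates that the primary-analysis section commits to report. Readers will take them as the size of the enhancement, and later studies may plan on them. The plan sets out not to assume when the effect peaks, so it cannot rely on a sharp peak to remove the bias.

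**Working it through.** **Inputs.** From the documents: five candidate minutes, selection of the largest positive difference, contrasts conditional on the interaction, and estimation from the same data. The documents state no sample size, SD, correlation, profile or numeric alpha, so there is no figure of the plan's to reproduce. Assumed: 20 per arm, SD 1, equal correlation ρ between minutes, complete data, interaction tested at 0.05.

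The values of ρ are 0.5 / 0.8 / 0.9. All change scores share one baseline. With equal independent errors of variance σ², two change scores have covariance σ² and variance 2σ², so ρ = σ²/2σ² = 0.5. Stable individual response raises this, so 0.5 is probably a low case.

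**Step 1: taking the maximum, no interaction condition, flat profile.** The part of the error common to all minutes does not affect which is largest. The mean of the largest of five independent standard normal values is 1.163, so

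bias = 1.163 × √(2/n) × √(1 − ρ).

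At n = 20, √(2/20) = 0.316, giving:

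- ρ = 0.5: 1.163 × 0.316 × 0.707 = 0.26 SD
- ρ = 0.8: 1.163 × 0.316 × 0.447 = 0.16 SD
- ρ = 0.9: 1.163 × 0.316 × 0.316 = 0.12 SD

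**Step 2: adding the plan's conditions.** Simulation, 40,000 trials per cell, keeping trials with a significant repeated-measures interaction F and a positive largest difference. The interval is the ordinary two-sample t interval at the selected minute. Three values are ρ = 0.5 / 0.8 / 0.9.

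| True differences at the five minutes (SD) | Bias against selected minute (SD) | Ordinary 95% CI coverage, selected minute | Bias against true maximum (SD) |
|---|---|---|---|
| Flat, 0 | +0.49 / +0.39 / +0.35 | 70% / 83% / 86% | same |
| Flat, 0.3 | +0.48 / +0.31 / +0.23 | 70% / 86% / 92% | same |
| Rounded: 0.2, 0.4, 0.5, 0.4, 0.2 | +0.38 / +0.21 / +0.12 | 82% / 92% / 95% | +0.32 / +0.16 / +0.09 |
| Sharp: 0, 0.3, 0.8, 0.3, 0 | +0.15 / +0.02 / +0.01 | 94–96% | +0.11 / +0.01 / +0.01 |

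Both conditions are met in only about 4–5% of flat-profile trials. The interaction is significant in about 13% / 28% / 54% of rounded-peak trials and 63% / 97% / 100% of sharp-peak trials. The flat rows therefore rest on about 40,000 × 0.04 to 0.05 = 1,600 to 2,000 trials, and repeat runs differ by up to about 0.02 SD and 2 coverage points.

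For the rounded peak at ρ = 0.5 the average reported effect is 0.50 + 0.32 = 0.82 SD. At ρ = 0.9 it is 0.50 + 0.09 = 0.59 SD.

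**Step 3: other sample sizes and correlation patterns.** These runs keep the interaction condition but omit the positivity condition, which if added raises the average estimate. Rounded peak, bias against the selected minute: +0.53 / +0.29 / +0.17 SD at 12 per arm and +0.29 / +0.14 / +0.07 SD at 30. With a shared baseline plus serially correlated errors (0.5 / 0.8) and a Greenhouse–Geisser test at 20 per arm, the bias is +0.32 / +0.20 SD.

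**Step 4: dropping the interaction condition.** Rounded-peak bias against the true maximum falls to +0.14 / +0.07 / +0.03 SD, with ordinary coverage of about 95%. Against the selected minute about +0.21 / +0.10 / +0.07 SD remains. Bonferroni intervals (1 − 0.05/5 = 99% each) at T* then cover 98–99% in every profile, on both benchmarks.

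**The case against.** **The interaction condition is partly inferred.** The sentence defining T* does not repeat it, and the objectives define T* without it. Without it, the rounded-peak bias against the true maximum is modest. This narrows the size, but the p-values that the T* definition uses arise only under the condition, so the conditional reading is the natural one. Bias from taking the maximum remains under either reading.

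**The large figures come from unfavourable assumptions.** This stands. Coverage near 70% needs a flat profile, correlation 0.5 and an interaction that is falsely significant. With a rounded peak and correlation 0.9, coverage is about nominal.

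**The other minutes may be visible.** The planned trajectories and between-group effect sizes may let a reader see the whole profile. That gives context but does not correct the figure at T*.

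**Three stronger readings do not hold:**

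- A reader might infer that Type I error is inflated. The confirmatory test is the repeated-measures ANOVA and the five contrasts are adjusted.
- A reader might infer that the interval at T* certainly undercovers. The plan does not say whether that interval is adjusted. If it is the ordinary one, coverage depends on profile, correlation and benchmark.
- A reader might infer that a dominant minute always removes the bias, or that bias is always material. The sharp peak still gives +0.15 SD at correlation 0.5, and almost none at 0.8 or 0.9.

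**Conclusion.** The concern holds as a matter of estimation and reporting, and should be fixed. The T* difference and Cohen's d are selected and estimated on the same data with no correction, so they tend to overstate the effect. The bias is negligible only when one minute dominates and the interaction is well powered, through high correlation between minutes or a large sample.

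High confidence applies to the direction alone. Under the assumptions shown for 20 per arm, the excess over the selected minute's true effect runs from about 0.01 SD (sharp peak, correlation 0.9) to about 0.49 SD (no true effect, correlation 0.5). The documents do not say where in that range this trial lies. The effect of carrying T* into the responder models was not computed.

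**What to change.** 1. Define T* by one criterion, the largest EXP–CON difference in estimated marginal means, so that the selection can be reproduced exactly.
2. Estimate and report all five between-group differences whether or not the interaction is significant, each with a Bonferroni simultaneous (99%) interval. Use that interval at T*. Name Bonferroni in both the primary-analysis and the multiplicity sections.
3. Label the T* difference and its effect size as descriptive of a minute chosen from the data, and state that they tend to overestimate. Steps 1 and 2 remove the part of the bias due to the interaction condition and restore coverage, but the bias from taking the maximum stays in the point estimate.
4. As a sensitivity analysis only, run a participant-level bootstrap, stratified by arm, that re-selects T* in each resample. Report the bias-reduced estimate and how often each minute is chosen. Do not attach the 99% interval to that estimate.

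**Cost.** Steps 1 to 3 are wording. The interval at T* is about one-third wider: 2.576/1.960 = 1.31 with normal quantiles, or 36% / 34% / 33% wider with t quantiles at 12 / 20 / 30 per arm. The bootstrap may need software beyond the two named packages. In checks at 20 per arm without the interaction condition, it cut rounded-peak bias at the selected minute from +0.21 / +0.10 / +0.07 to +0.05 / +0.01 / +0.01 SD. Against the true maximum it over-corrected, by up to 0.05 SD for the rounded and 0.08 SD for the sharp peak, so it should not replace the main estimate.

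### The T* difference is tested with a five-minute correction but reported with a 95% CI not stated to be adjusted, so the interval can exclude zero when the adjusted test is not significant

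*Combined protocol and SAP*

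**What the plan says.** The section on the primary analysis and the peak time T* sets out four steps.

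- **Gate.** The contrasts follow only a significant Group × Time interaction: "If the interaction is significant, we estimate adjusted between-group contrasts at each minute".
- **Correction.** The five minutes form one family, handled "with Bonferroni correction across the five time points".
- **Selection.** "T^* is defined as the minute showing the largest positive EXP–CON difference in estimated marginal means (EMMs) with the smallest p-value".
- **Report.** "We report the EMM difference at T^* (95% CI", together with a standardised effect size.

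The section on assumptions, multiplicity and robustness names a different procedure for the same family: "Multiplicity is controlled via Holm across the five between-group contrasts".

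The section on reporting, visualization and software again refers to 95% intervals without mentioning adjustment: "Figures include EMM trajectories with 95% CIs".

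The document states neither alpha nor sidedness. It also gives no sample size, SD or correlation between minutes.

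**The concern.** A p-value and a confidence interval for the same contrast should normally lead to the same conclusion. Here the p-value is corrected for five looks. The interval, on its plain reading, is an ordinary one matching an uncorrected 5% test. Between the two thresholds, the trial's main estimate would come with a non-significant adjusted p-value beside an interval wholly above zero.

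Selection adds to this. T* is picked because its difference is the largest of five, so an ordinary interval at T* covers the true difference less often than 95%. The primary objective asks whether PAPE occurs somewhere in the 4–12 min window, and the T* difference is the estimate that answers it. Readers will look at that interval first.

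**Working it through.** The plan gives no figure of its own to reproduce, so the check has three parts: the thresholds, the coverage at T*, and the frequency of disagreement.

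**1. Thresholds**

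Inputs: five contrasts (minutes 4, 6, 8, 10, 12; from the plan); alpha 0.05 two-sided (assumed).

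- Per-minute level: 0.05 / 5 = 0.01, so |z| must reach 2.576.
- An ordinary 95% CI excludes zero when |z| > 1.960, that is, raw p < 0.05.
- Band of disagreement: raw p between 0.01 and 0.05.
- Interval that matches the test: 1 − 0.05/5 = 99% per minute.

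Two examples, with limits in units of the standard error (z ± 1.960 and z ± 2.576):

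| Raw p | z | Bonferroni p = 5 × p | 95% CI | 99% CI |
|---|---|---|---|---|
| 0.02 | 2.326 | 0.10 | 0.37 to 4.29 | −0.25 to 4.90 |
| 0.03 | 2.170 | 0.15 | 0.21 to 4.13 | −0.41 to 4.75 |

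In both rows the adjusted test is not significant, the ordinary interval excludes zero, and the matching interval includes it.

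*Other values of alpha, and one-sided tests.* Alpha 0.10 gives 0.10 / 5 = 0.02, a 98% interval and a band of 0.02–0.05. Alpha 0.01 gives 0.002, a 99.8% interval and a band of 0.002–0.05. A one-sided 0.05 test gives 0.01 one-sided per minute, which is a two-sided p of 0.02, so the band is 0.02–0.05. The mismatch remains in each case.

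*Holm in place of Bonferroni.* Holm tests the smallest of the five p-values at 0.05 / 5 = 0.01, so the band is the same whenever T* has the smallest p-value. If the largest difference and the smallest p-value fall at different minutes, Holm's threshold at T* can be looser (0.0125 at the second step, up to 0.05 at the last).

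**2. Coverage at T***

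Assumptions (none in the document): 15–30 per group, equal SDs, equal correlation of 0.3–0.8 between minutes, no effect at any minute.

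Before the gate, the ordinary 95% CI at the largest difference lies wholly above zero in roughly 6–10% of trials, where 2.5% would be expected for a single prespecified minute. Coverage is therefore about 90–94%. It is lower among trials that pass the gate, because the gate favours data with an extreme minute. The 99% interval lies wholly above zero in about 1–2.5% of ungated trials.

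**3. Frequency of disagreement**

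Same assumptions, with a true difference of 0.7 SD at 8 min and 0.3 SD at 6 and 10 min, and a Greenhouse–Geisser Group × Time gate at 0.05. Share of gated trials in which the 95% CI excludes zero but the Bonferroni test is not significant:

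| n per group | correlation 0.3 | 0.5 | 0.8 |
|---|---|---|---|
| 15 | 0.306 | 0.276 | 0.260 |
| 20 | 0.269 | 0.265 | 0.259 |
| 30 | 0.190 | 0.232 | 0.244 |

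That is about 20–31%; repeat runs move individual cells by one to three percentage points. At n = 20 and correlation 0.5, the CI excludes zero in 76% of gated trials and the Bonferroni test is significant in 49%: 76 − 49 = 27%. As a share of all trials, gated or not, the disagreement is about 7–24%.

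With no effect at any minute, passing the gate and also having the 95% CI above zero happens in about 0.4–1.7% of trials (up to 1.9% in a repeat run).

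**The case against.** **The interval may already be adjusted.** The plan says "we estimate adjusted between-group contrasts at each minute with Bonferroni correction across the five time points", and this could be read as covering the intervals too. In that case there is no conflict. The reading is possible, but the sentence about the T* result does not carry it over, so the plan should say which is meant.

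**The corrected test decides, and the interval only describes.** This largely stands. A reader might infer that the plan leaves open whether the p-value or the interval settles the question. The document does not support that: it places the corrected contrasts inside the confirmatory analysis and never uses the interval as a decision rule. What remains is that the descriptive interval is unlabelled and can point the other way.

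**The interaction gate protects against false claims.** A reader might infer that using the interval raises the false-positive rate to 6–12%. That range ignores the gate, which the plan requires before any T* result exists, and 11.8% arises only at zero correlation. With the gate and no effect at any minute, the figure is about 0.4–1.7%. The gate does not remove the disagreement when the groups truly differ over time, and the 20–31% is already conditional on it. In that scenario an effect exists, so those disagreements are not false claims.

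**The trajectory figure shows the same fault.** A reader might count it as further evidence. It most naturally shows each group's means over time, and such intervals need not match a between-group test. It does not add to the point.

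**Conclusion.** The point holds as a mismatch between the adjusted test and the interval reported beside it, on the plain reading that the 95% CI is an ordinary one. The band of raw p from 0.01 to 0.05 follows from the five contrasts and an assumed two-sided alpha of 0.05. It applies under Holm as well when T* has the smallest p-value. The interval also ignores the selection of T*, with coverage of about 90–94% under no effect and before the gate.

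The 20–31% (7–24% of all trials) depends on an assumed effect pattern, sample size and correlation, and should be read as an order of magnitude. The adjusted test itself is not invalidated, and the point does not show that the trial's false-positive rate is out of control. It merits correction because the interval concerned belongs to the main result and the change is small.

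**What to change.** 1. Name one procedure for the five contrasts, the same in the primary analysis section and the multiplicity section. Bonferroni is the practical choice because it has simple matching intervals. If Holm were kept, 99% intervals at all five minutes would not match it: a later-ranked minute could be Holm-significant while its 99% CI includes zero.
2. State alpha and sidedness.
3. Report the EXP–CON difference at T* and at the other four minutes with Bonferroni simultaneous 95% CIs (99% per minute at two-sided alpha 0.05).
4. State that the adjusted p-value is the decision rule and that these intervals agree with it.
5. Label any ordinary 95% CI as adjusted neither for the five minutes nor for the selection of T*.

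Group-mean intervals in the trajectory figure need no change.

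Simultaneous intervals allow for choosing among the five minutes. They do not correct for reporting only after a significant interaction, so giving all five differences whatever the gate result would be a useful addition.

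**Cost.** A few sentences of text. The intervals become about 30–35% wider (2.576 / 1.960 = 1.31; with t quantiles, 1.35 at 28 df and 1.33 at 58 df). Holm's small power advantage at the later-ranked minutes is given up.

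### The within-EXP time-course analysis compares the post-intervention minutes only with each other: no prespecified within-group test sets mean ΔCMJ against zero, and the named peak need not lie above baseline

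*Combined protocol and SAP*

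**What the plan says.** *Objectives and endpoints* makes the EXP curve an endpoint: "Secondary endpoints include the time-course of ΔCMJ within the experimental group (EXP". The same section defines the change in jump height "at post-intervention time points (4, 6, 8, 10, 12 min", and *Data handling and derived variables* adds that "ΔCMJ and percentage change (% ΔCMJ) will be computed relative to baseline".

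*Within-group time-course and kinetics* gives the analysis and its aim. The aim is "To describe the temporal profile without prespecifying a target minute", the test is "we analyse ΔCMJ across time within EXP using a one-way repeated-measures ANOVA" (with a mixed model as fallback), and it is "followed by Bonferroni-adjusted pairwise EMMs to locate the within-group peak". For individual athletes, "we model time to first and time to peak response (4–12 min) using Kaplan–Meier curves with censoring at 12 min".

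*Phenotype and morphology linkages* carries the approach to ultrasound as a "within-EXP time-course (rmANOVA/LMM with Tukey" analysis and says that TMG and EMG follow the same framework.

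*Reporting, visualization, and software* plans means with 95% confidence intervals, within-subject effect sizes, plots of the estimated marginal means (EMMs) over time with 95% intervals, and individual waterfall plots showing the MDC. No section plans a test of mean ΔCMJ in EXP against zero, or requires the within-group peak to be above zero.

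**The concern.** Each ΔCMJ value is a change from baseline, so the natural first question about the EXP curve is whether it lies above zero, and at which minutes. The planned F test and pairwise comparisons do not ask this. They ask whether the curve is flat. Two misreadings follow.

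- If jumps are higher by the same amount at every minute, the analysis returns no time effect, which is easily reported as no enhancement.
- If jumps are depressed at 4 min and merely recover by 12 min, the analysis returns a time effect and a peak, which is easily reported as enhancement.

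What is at stake is the conclusion drawn from a named secondary endpoint. The primary comparison of EXP with CON is not affected.

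**Working it through.** **Inputs from the documents.** Outcome: ΔCMJ. Levels: 4, 6, 8, 10 and 12 min, so k = 5. Post-hoc tests: minute against minute. The documents give no sample size, SD, effect size or correlation, so there is no planned figure to reproduce.

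**Step 1: a constant gain cancels exactly.** Let y_ij be ΔCMJ for athlete i at minute j, with n athletes.

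- SS_time = n Σ_j (ȳ_.j − ȳ_..)²
- SS_error = Σ_i Σ_j (y_ij − ȳ_i. − ȳ_.j + ȳ_..)²
- F = [SS_time / 4] / [SS_error / (4(n − 1))]

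Add a constant c to every y_ij. In SS_time, (ȳ_.j + c) − (ȳ_.. + c) is unchanged. In SS_error, c − c − c + c = 0. Every pairwise difference also loses c. So neither F nor any minute-to-minute contrast depends on c, whatever n or the SD.

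In one simulated data set with n = 20 (baseline SD 5 cm and error SD 1.2 cm, both assumed), F(4,76) = 0.754, p = 0.558, for gains of 0, 1, 2 and 5 cm alike. At the 1 cm gain, each athlete's mean ΔCMJ tested against zero gives t = 4.56, p = 0.0002.

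**Step 2: rejection rates under a constant gain.** With gains of 0 to 3 cm and n = 12 to 40 (4,000 runs per setting), the planned ANOVA rejected in 4.4% to 5.7% of runs, which is its type I error. The Bonferroni pairwise tests found any difference in about 2% to 5% (800 runs per setting).

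**Step 3: the reverse case.** Let mean ΔCMJ rise from −1 SD at 4 min to 0 at 12 min, so that EXP never exceeds baseline on average. The ANOVA is then significant in 85% of runs at n = 12 and 99.9% at n = 30 (correlation 0.5 between minutes, assumed).

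**Step 4: what a test against zero adds.** Take a constant gain of δ SD of ΔCMJ and a two-sided level of 0.05 / 5 = 0.01 at each minute. Power at a given minute comes from the noncentral t distribution with n − 1 degrees of freedom and noncentrality δ√n; for example, 0.5 × √12 = 1.73 and 1.0 × √12 = 3.46. The chance that at least one of the five minutes is significant was simulated with correlation 0.5. That correlation is what independent errors of equal variance at baseline and at each minute would give: σ² / (2σ²) = 0.5.

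| n in EXP (assumed) | Planned ANOVA | Any given minute, δ = 0.5 to 1.0 | At least one of five minutes, δ = 0.5 to 1.0 |
|---|---|---|---|
| 12 | about 5% | 14-64% | 40-93% |
| 20 | about 5% | 30-93% | 66-99.8% |
| 30 | about 5% | 50-99.5% | 84-100% |

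With correlation 0.8, the last column at n = 12 falls to about 29-86%. With no gain, the five adjusted tests reject in about 4% of runs at correlation 0.5. All five minutes are significant together much less often: about 0.7-27%, 4-78% and 16-98% at n = 12, 20 and 30.

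**Step 5: other planned within-EXP analyses.** Kaplan-Meier, log-rank and Cox methods concern the timing of individual responses. Correlation, moderation and mediation concern association. The responder χ² test compares EXP with CON. None tests the EXP mean against zero. The mixed-model fallback has the same gap unless its EMMs are tested against zero.

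**The case against.** The strongest reply is that the ANOVA does what it was written for. Its stated aim is the temporal profile and the peak, and a test of differences between minutes suits that. Whether the conditioning activity works is the EXP-CON question. This stands, and it is why the point is an improvement to a secondary analysis and not an error in the main one. But a peak is to be named from this curve, and a peak of enhancement has little meaning unless the curve is above zero there.

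Four stronger readings are tempting, and the documents do not support them.

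- *That the analysis has no baseline reference.* ΔCMJ is itself baseline-referenced. What is missing is a test of it against zero.
- *That a sustained gain would go unseen.* The planned 95% intervals, if on the ΔCMJ scale, would lie above zero. The waterfall plots and first-response curves would also show it, and a constant EXP-CON difference would appear in the Group main effect of the primary model. What is missing is a multiplicity-adjusted decision rule. The gap is somewhat sharper because the minute-by-minute EXP-CON contrasts follow only a significant Group × Time interaction, which a constant difference does not produce.
- *That ultrasound and TMG share the defect.* The plan does not list the time levels for the ultrasound analysis and makes change scores optional for TMG, so raw values with a baseline level remain possible. Only EMG is explicitly given as percentage change at 4 to 12 min.
- *That baseline as a sixth level would be an equivalent remedy.* On the ΔCMJ scale it is a column of zeros with no variance. On raw CMJ it is a different test: at n = 12 and a 1 cm gain, the six-level F test had power 0.45, against 0.52 for at least one of five adjusted tests against zero.

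**Conclusion.** The gap is real and limited. The cancellation in Step 1 is exact and rests on no assumption: under a constant gain the planned ANOVA keeps its type I error rate of about 5% at any n. The possibility of naming a peak in a group that never rose above baseline follows from the absence of any condition on the sign of the peak. How often that happens, and how much a test against zero gains, depend on group size, effect size and correlation, all of which are assumed here. The at-least-one-minute figures should not be read as the chance of establishing enhancement at every minute. The matter affects what the secondary endpoint can conclude within EXP. It does not alter the primary inference.

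**What to change.** In *Within-group time-course and kinetics*:

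1. Keep the one-way ANOVA and describe it as a test of the shape of the curve.
2. Add the EMM of ΔCMJ against zero at each of the five minutes, from the same model, Bonferroni-adjusted over five, with matching adjusted intervals.
3. Name a within-group peak of enhancement only if its EMM exceeds zero after adjustment.
4. State that a null time effect does not mean no enhancement.
5. Apply the same rule to EMG, and to ultrasound and TMG if they are analysed as change scores without a baseline level. State which levels those analyses use.
6. Reserve any claim of an effect of the conditioning activity for EXP-CON contrasts, because a rise over baseline in one group cannot be attributed to the intervention alone.

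The cost is one set of contrasts and a few sentences. No new data or athletes are needed.
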